### **13.3 Analysis Population**

#### ***13.3.1 Intent-To-Treat Population***

The Intent-to-Treat (ITT) target population will include all subjects in the target population who are randomised, irrespective of any deviation from the protocol or premature discontinuation. The treatment group assignment will be designated according to initial randomisation. The ITT target population will serve as the basis for the formal analysis of efficacy. The overall ITT population will include all subjects in both the target and off-target populations (Group A + Group B) who are randomised, irrespective of any deviation from the protocol or premature discontinuation. The overall ITT population will be used for supportive efficacy analyses.

### **13.3.2 Safety Population**

The target Safety Population will include all randomised subjects in the target population who receive at least one dose of study drug. The treatment group assignment in this population will be defined by the treatment actually received. This population will be used for the evaluation of safety in the target population. The overall Safety Population will include all randomised subjects in both the target and off-target population who receive at least one dose of study drug. The overall Safety Population will be used for supportive evaluations of safety.

### **13.4 Demographic and Baseline Characteristics**

Demographic data and other baseline characteristics including medical history will be analysed based on the target safety population. Summary statistics will be provided for all collected variables. Continuous variables will be summarized by descriptive statistics, including mean, SD, median, minimum, and maximum. Details of endpoint analyses will be described in the SAP.

### **13.5 Investigational Medicinal Products**

The duration (days) of exposure of givinostat/placebo will be calculated for each subject in the target and overall populations, and will be summarized descriptively including the mean, SD, median, minimum, and maximum by treatment group and overall.

In addition, the daily dosage (mg) of givinostat will be summarized for each subject in the target and overall populations, and will be summarized descriptively including the mean, SD, median, minimum and maximum.

Reason for treatment discontinuation and number of subjects treated beyond protocol-specified discontinuation criteria will also be summarized in the target and overall populations. Summaries will be based on the respective safety population.

### **13.6 Prior and Concomitant Therapy**

Prior treatments, defined as those taken within 6 months prior to screening, should be recorded in the source documents as prior medications.

Concomitant treatments are defined as treatments taken after study drug administration.

Prior and concomitant medications will be classified using the WHO-DRL drug dictionary (using the most recent version) and summarised in the target and overall populations. Summaries will be based on the respective safety population.

### **13.7 Efficacy Analysis**

All formal efficacy analyses will be performed on the ITT target population; efficacy analyses in the overall population will be supportive and informal. Descriptive statistics for qualitative data will include frequency tabulation and presentation of percentages. Descriptive statistics for quantitative data will include mean and SD or geometric mean, coefficient of variation, median and interquartile range.

#### ***13.7.1 Analysis of the Primary Efficacy Endpoint***

The change in 4SC from baseline to 18 months will be evaluated in the target population. The data will be analyzed using an Analysis of Covariance (ANCOVA) model with the change in 4SC from baseline to 18 months as the dependent variable and with terms for baseline 4SC value as a covariate and randomised treatment, concomitant steroid use and age at baseline as independent class variables. Least squares means will be estimated for givinostat and placebo. The treatment effect, being the difference in Lsmeans, will be presented along with the associated 95% confidence interval and the p-value. Significance will be achieved if the 1-sided p-value is  $\leq 0.025$ .

#### ***13.7.2 Analysis of Key Secondary Efficacy Endpoints***

##### Analysis of Key Secondary Endpoints

Formal analyses of functional key secondary endpoints (i.e., cumulative loss of function in the NSAA, change in 6MWT, NSAA, time to rise from floor and muscle strength by knee extension and elbow flexion) and Vastus lateralis MFF will take place in the target population at 18 months and will be achieved using the same approach as described for the primary /endpoint. Possible need for log transformation of these variables will be assessed prior to unblinding by assessment of ANCOVA model residuals without a treatment effect term.

### ***13.7.3 Analysis of Exploratory Efficacy Endpoints***

Exploratory efficacy endpoints will be supportive only and not subject to alpha control; therefore nominal p-values will be presented.

The mean change from baseline to 18 months will be compared between givinostat and placebo in the target population for:

- Time to walk/run 10 meters;
- Quality of life assessed by Paediatric Outcomes Data Collection Instrument (PODCI);
- %-predicted 6MWT;

These endpoints will be analyzed using methods in line with those described for the primary and key secondary endpoints.

The fraction of subjects achieving the following endpoints at 18 months will be compared between givinostat and placebo in the target population:

- Proportion of subjects with  $\geq 10\%$  worsening in 6MWT at end of study;
- Proportion of subjects who loose ambulation during the study.

These endpoints will be analysed using a logistic regression model with terms for randomised treatment, concomitant steroid use and age at baseline. The odds for each treatment group will be extracted along with the odds ratio, associated 95% confidence interval and p-value.

The following endpoints will be compared between givinostat and placebo in the target population using Cox proportional hazards modelling:

- Time to 10% persistent worsening in 6MWT (Baseline through end of study);
- Time to loss of standing (Baseline through end of study);

The model will include terms for randomised treatment, concomitant steroid use and age at baseline. The hazard ratio will be extracted, along with the associated 95% confidence interval and p-value.

Moreover, exploratory analyses will be done in the target population to explore whether the effects of givinostat versus placebo administered chronically may be related to the type of DMD mutation, LTBP4 and Osteopontin genotype or to the biomarkers.

### **13.8 Pharmacokinetic Analysis**

Nonlinear mixed effect models will be used for the evaluation of the population PK profile. The population PK analysis will be performed using NONMEM software (Version VI or later).

The evaluation will be performed for describing the PK of givinostat and its major metabolites (ITF2374 and ITF2375) in the subject population and for identifying the relevant demographic and pathophysiological covariates. Separate PK models for givinostat and its metabolite will be developed.

Additionally, the relationship of givinostat PK exposure to efficacy and safety endpoints in the target population will be explored as exploratory analyses.

The Population PK approach will be based on the development of the following 3 models:

1. Identification of the structural model that best describes the PK data in absence of covariates;
2. Random Effect Models: defining the inter-individual variability and the residual error. Different forms of residual error (additive, multiplicative or both) will be explored;
3. Covariate Model: identifying the relevant demographic and pathophysiological covariates affecting the PK profile of the compound. The selection of the covariates will be performed using an appropriate statistical methodology.

Population PK procedures and analyses will be detailed in a separate “Population PK data analysis plan.”

### **13.10 Interim Analysis**

A single interim analysis is planned and will be performed by the IDMC in the target population. An IDMC charter will be prepared to describe the role, function and operations of the IDMC and the rules to be used when reviewing interim data.

#### **13.10.1 Interim Analysis**

The interim analysis will be performed when the first N=50 subjects randomised in the target population have reached the 12 month time point. In this interim analysis, the IDMC will evaluate the effects of givinostat versus placebo on the vastus lateralis MFF (VL MFF) in terms of futility. Futility will be considered if the mean change from baseline to 12 months in VLMFF in the givinostat group is equal to or worse than that seen in the placebo group since the biologic plausibility of a subsequent treatment effect on 4SC time would be greatly diminished. The IDMC will only communicate to the Sponsor whether the study should proceed or it should be stopped having met the futility criteria.

If the IDMC indicates that the study should proceed, a blinded sample size re-estimation will be conducted for MFF and 4SC in the target population as follows:

- To maintain the blind on the primary endpoint, the within treatment SD for the change from baseline will be estimated as  $\hat{\sigma}_{within} = \sqrt{\hat{\sigma}_{overall}^2 - \left(\frac{\Delta}{2}\right)^2}$  where  $\hat{\sigma}_{overall}$  is the overall SD for the change from baseline in 4SC based on the n=50 subjects in

the interim and  $\Delta$  is the originally hypothesized treatment effect, i.e.,  $\Delta = 3$  seconds. Dependent upon the blinded SD estimate, the sample size may be decreased or increased to maintain 90% power. Any increase in sample size for 4SC will be limited to 1.5 times maximum of the initial target population sample size, i.e., to a maximum of  $1.5 \times 192 = 288$  subjects. For a 20% increase in the SD, this degree of increase in sample size will maintain 90% power, and for a 40% increase in SD power will be maintained at 80%.

- With respect to VL MFF, a similar approach will be applied; the within treatment SD for the change from baseline will be estimated as  $\hat{\sigma}_{within} = \sqrt{\hat{\sigma}_{overall}^2 - \left(\frac{\Delta}{2}\right)^2}$  where  $\hat{\sigma}_{overall}$  is the overall SD for the change from baseline in VL MFF and  $\Delta$  is the originally hypothesized treatment effect, i.e.  $\Delta = 3.63\%$  (i.e., 55% of 6.6%). Dependent upon the blinded SD estimate, the sample size may be decreased or increased to maintain 90% power. Any increase in sample size required to assess MFF will also be limited to 1.5 times the required target population sample size stated in the preceding power calculation, to a maximum of  $1.5 \times 99 = 150$  subjects.

At the interim futility analysis, there will be no efficacy assessment, no unblinded analysis of the primary endpoint and, hence, no alpha spend nor early stopping of the study for efficacy.

As noted above in Section 13.2, the interim analysis took place in January 2020; futility was passed and the blinded sample size reassessment followed. The estimated SD for 4SC was approximately half of that assumed in the original power calculation. Consequently, it was determined that a total of N=102 patients would be sufficient to test the hypothesis that 4SC was improved by at least 2 seconds with givinostat compared placebo. With allowance for a small dropout rate, a total of 110 male ambulant subjects will be randomised in the target population (Group A). Up to 50 subjects (about 35% of the overall population) outside of the target may also be recruited into the study (Group B). The overall subjects population (Group A + Group B) will provide supportive data.

For the MR cohort, the blinded SD estimate was 5.941%, being in line with SD assumed in the original power calculation for VL MFF, hence all the subjects in the target population will be included in the analysis of the MR cohort.

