## 1 SYNOPSIS

Title of Study:	Randomised, double blind, placebo controlled, multicentre study to evaluate the efficacy and safety of givinostat in ambulant patients with Duchenne Muscular Dystrophy
Acronym	EPIDYS – Epigenetic Rescue of Dystrophin Dysfunction
Protocol Number:	DSC/14/2357/48
Study Design:	Randomised, double blind, parallel group, placebo controlled study. Subjects will be randomised 2:1 to givinostat or placebo.
Investigators/Study Sites:	Approximately 50 sites worldwide
Phase of Development:	3
Objectives:	
Primary objective:
 
 
To establish the effects of givinostat versus placebo administered chronically over 18 months to slow disease progression in ambulant DMD subjects.
 
 
Secondary objectives:
 
 
To assess the safety and tolerability of givinostat versus placebo administered chronically in DMD subjects.
 
To evaluate the pharmacokinetic (PK) profile of givinostat administered chronically in DMD subjects;
 
To evaluate the impact on quality of life and activities of daily living of givinostat versus placebo administered chronically.
 
 
Secondary exploratory objectives:
 
 
To evaluate the correlation between PK profile of givinostat and pharmacodynamics (PD) data;
 
To explore whether the effects of givinostat versus placebo administered chronically may be related to the type of DMD mutation or to the biomarkers.
 

Study Population and Subset Definition:	
Ambulant male paediatric subjects aged <math>\geq 6</math> years at baseline affected by DMD will be included in this study.
 
Target population (Group A): subjects with a baseline vastus lateralis muscle fat fraction (VL MFF) assessed by MRS in the range <math>>5\%</math> and <math>\leq 30\%</math>.
 
Off-target population (Group B): subjects with a baseline vastus lateralis muscle fat fraction (VL MFF) assessed by MRS in the range <math>\leq 5\%</math> or <math>>30\%</math>.
 
MR Cohort: all subjects in the target population who will perform the magnetic resonance assessment at baseline, 12 and 18 months.

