	
degree of increase in sample size will maintain 90% power, and for a 40% increase in SD power will be maintained at 80%.
 
 
• With respect to VL MFF, a similar approach will be applied; the within treatment SD for the change from baseline will be estimated as <math>\hat{\sigma}_{within} = \sqrt{\hat{\sigma}_{overall}^2 - \left(\frac{\Delta}{2}\right)^2}</math> where <math>\hat{\sigma}_{overall}</math> is the overall SD for the change from baseline in MFF and <math>\Delta</math> is the hypothesized treatment effect, i.e. <math>\Delta = 3.63\%</math> (i.e. 55% of 6.6%). Dependent upon the blinded SD estimate, the sample size may be decreased or increased to maintain 90% power. Any increase in sample size require to assess VL MFF will also be limited to 1.5 times the required target population sample size stated in the preceding power calculation, to a maximum of <math>1.5 \times 99 = 150</math> subjects.
 
 
At the interim futility analysis, there will be no efficacy assessment, no unblinded analysis of the primary endpoint and, hence, no alpha spend nor early stopping of the study for efficacy.
 
The interim took place as planned on 14th January 2020 and included 50 patients with 12 month data and 37 with 18 month data. The independent data monitoring committee (IDMC) meeting to review the VL MFF data for futility took place on 23rd January 2020 and concluded that futility was not met and the trial should continue. The sample size reassessment therefore took place, with estimated overall SDs of 3.094 seconds and 5.941% for the change from baseline in 4SC at 18 months and the change from baseline in VL MFF at 12 months respectively.
 
The revised sample size (utilizing a 2:1 randomisation scheme) N=102 was calculated to provide 90% power and a 1-sided alpha of 2.5% to detect a true difference between givinostat and placebo in the target population, in 4SC 18 month change from baseline, of 2 seconds, with the blinded SD estimates during the interim analysis of 3.094 seconds. With an estimated drop-out rate of 8%, a total of 110 subjects in the target population (Group A) will be randomized.
 
For the MR cohort, since the blinded SD estimate was 5.941%, all the subjects in the target population will be part of the MR cohort.
 
Since the interim only assessed futility on VLFF and executed a blinded sample size reestimation, no alpha was spent and, hence the analysis of the primary endpoint conducted at the end of the trial will continue to be assessed at the 0.025 1-sided level.

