natural history database (Data on File), which showed that a change of 1 to 1.5 seconds in TFTs has clinical meaningfulness based on health-related QoL and participation measures in DMD and that a 1.6 to 1.7 second change over 12-months in TFTs translates to a 3-year prolongation of ambulation in DMD. Together, these new data suggest that 2 seconds is an appropriate conservative estimate of a clinically meaningful effect size for TFTs in DMD, which is less than the 3 seconds originally hypothesized in the study protocol (MCID; McDonald CM et al. 2013); however, with the blinded SD estimate made at the planned interim, the revised total number of subjects, N=102 has 90% power to detect this smaller, yet clinically relevant treatment effect. The treatment duration of 18 months has been chosen because DMD children with more preserved muscle mass will be enrolled in this study, and despite the underlying progression of muscle tissue deterioration, a decline of function is expected to be slower in the selected patient population compared to DMD subjects in “decline phase” (e.g., DMD subjects >7 years with 6MWT < 350 meter, McDonald, Henricson et al. 2013); thus, a longer observation period is needed to demonstrate functional benefits compared givinostat to placebo controls.

At randomisation, the population will be stratified according to steroid type and regimens (i.e., daily regimen or intermittent regimen) because some evidence suggests Deflazacort use was associated with later loss of ambulation and increased frequency of side effects (Bello et al. 2015) and daily administration of steroids to be more effective than treatment on alternate days (Bushby, Finkel et al. 2010^34; Ricotti, Baranello et al. 2013). Thus, to help to ensure balance between the randomised treatment arms stratification by steroid type and regimens will be implemented.

Daily regimen means every daily intake of steroids, while intermittent regimens comprise steroids used every other day, high dose weekend and 10 days on alternate to 10 or 20 days off. Different schedule can be discussed with the Medical Monitor before the subject randomisation, however the decision remains with the Investigator only or its authorized designee.

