- ii. With respect to VL MFF, a similar approach will be applied; the within treatment SD for the change from baseline will be estimated as $\hat{\sigma}_{within} = \sqrt{\hat{\sigma}_{overall}^2 - \left(\frac{\Delta}{2}\right)^2}$ where $\hat{\sigma}_{overall}$ is the overall SD for the change from baseline in VL MFF and Δ is the originally hypothesized treatment effect, i.e. $\Delta = 3.63\%$ (i.e., 55% of 6.6%). Dependent upon the blinded SD estimate, the sample size may be decreased or increased to maintain 90% power. Any increase in sample size required to assess VL MFF will also be limited to 1.5 times the required target population sample size stated in the preceding power calculation, to a maximum of $1.5 \times 99 \approx 150$ subjects.

To ensure that the blind is maintained for the sample size re-estimation, this will be completed by a blinded statistician at Veristat. The IDMC will then formally communicate the outcome of the sample size re-estimation.

At this interim futility analysis, there will be no efficacy assessment and no unblinded analysis of the primary endpoint and, hence, no alpha spend nor early stopping of the study for efficacy.

Details of the outputs to be produced at the interim analysis are given in Appendix 7.7. Shells for the outputs to be produced at this interim analysis are included in a separate 'Interim Analysis 1 Table, Figure and Listing Shells' document.

As noted above in Section 2.5, the interim analysis took place in January 2020; futility was passed and the blinded sample size reassessment followed. The estimated SD for 4SC was approximately half of that assumed in the original power calculation. Consequently, it was determined that a total of N=102 patients would be sufficient to test the hypothesis that 4SC was improved by at least 2 seconds with givinostat compared with placebo after 18 months of treatment. With allowance for a small dropout rate, a total of 110 male ambulant subjects will be randomised in the target population (Group A). Up to 50 subjects (about 35% of the overall population) outside of the target may also be recruited into the study (Group B). The overall subjects population (Group A + Group B) will provide supportive data.

For the MR cohort, the blinded SD estimate was 5.941%, being in line with the SD assumed in the original power calculation for VL MFF. Therefore, all the subjects in the target population will be included in the analysis of the MR cohort.

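### The blinded SD formula uses the 1:1 allocation term in a 2:1 trial, so it gives a within-treatment SD about 0.5% to 1.7% below the 2:1 formula; the effect on 4SC is 1 to 3 patients

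*Protocol*

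**What the plan says.** The trial's allocation is unequal: "Subjects will be randomised 2:1 to givinostat or placebo" (Protocol synopsis). The re-estimation rule appears in the Protocol synopsis (Statistical Methods and Planned Analyses), Protocol 13.10.1 and SAP 2.6. For 4SC it reads: "To maintain the blind on the primary endpoint, the within treatment SD for the change from baseline will be estimated as" sqrt(overall SD^2 - (Delta/2)^2). In 13.10.1 Delta "is the originally hypothesized treatment effect, i.e". 3 seconds. For VL MFF, SAP 2.6 says that "a similar approach will be applied; the within treatment SD for the change from baseline will be estimated as" the same expression, with Delta = 3.63%. No section adapts the expression to 2:1.

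The result is reported as follows. The synopsis states that "N=102 was calculated to provide 90% power and a 1-sided alpha of 2.5" per cent, on a 2:1 basis, for a difference of 2 seconds. Protocol 6.2 supports that target: "2 seconds is an appropriate conservative estimate of a clinically meaningful effect size for TFTs in DMD". The interim 4SC SD of 3.094 s is called an overall SD in the synopsis under Statistical Methods. It is called a within-treatment SD in the synopsis sample size entry, Protocol 6.2 and 13.2, and SAP 2.5. For VL MFF, the interim SD of 5.941% was judged in line with the assumed 6%, and every target-population subject was placed in the MR cohort. No new VL MFF sample size was derived.

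**The concern.** A blinded SD pools both arms, so its variance contains the within-arm variance plus a between-arm part that depends on the allocation. To recover the within-arm SD, that part has to be subtracted in the form that fits the design. The plan subtracts the 1:1 form and then sizes the trial at 2:1, so two linked steps of one calculation assume different allocations. The planned ratio is public and can be used without breaking the blind, so blinding does not explain the choice.

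What is at stake is the accuracy of the SD, and through it the N or power claimed for the primary endpoint. The formula also remains the documented method in both protocol and SAP.

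**Working it through.** **Inputs.** Allocation 2:1; 1-sided alpha 2.5%; 90% power for 4SC (synopsis). Target 2 s, original assumption 3 s with SD 6 s (Protocol 6.2, 13.2). Interim SDs 3.094 s and 5.941%. VL MFF Delta 3.63%, with N=99 at 80% power and SD 6% (SAP 2.5).

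**The correct term.** With share p in one arm and a mean difference Delta, overall variance = within variance + p(1-p) x Delta^2.
- 1:1: p(1-p) = 1/4, which gives (Delta/2)^2.
- 2:1: p(1-p) = (2/3)(1/3) = 2/9.
- Excess subtracted: (1/4 - 2/9) x Delta^2 = Delta^2/36. This is 0.25 s^2 at Delta = 3 s, 0.11 s^2 at Delta = 2 s, and 0.366 (%^2) for VL MFF.

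**The plan's own sizes.** At 2:1, total N = 4.5 x SD^2 x (z_alpha + z_beta)^2 / d^2, rounded up to whole blocks of three.
- Original 4SC: 4.5 x 36 x 10.507 / 9 = 189.1, giving 192. Reproduced.
- Original VL MFF: 4.5 x 36 x 7.849 / 13.177 = 96.5, giving 99. Reproduced.
- Revised 4SC: N=102 is reached at 2:1 if 3.094 is the overall SD and the printed formula is used with Delta = 2. SD = sqrt(9.573 - 1) = 2.928; N = 101.3, giving 102; power at 102 is 90.2%.
- The written Delta = 3 gives 87. Treating 3.094 as the within-treatment SD gives 114 at 2:1, with 86.8% power at 102. A 1:1 calculation with 3.094 as the within-treatment SD also gives 102, but the documents say 2:1.

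**4SC with the 2:1 term (normal approximation, 2 s, 90% power).**

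| Reading of 3.094 s | SD, printed | SD, 2:1 | N unrounded | N in blocks |
|---|---|---|---|---|
| Overall, Delta = 2 | 2.928 | 2.947 (+0.65%) | 101.3 to 102.7 | 102 to 105 |
| Overall, Delta = 3 | 2.706 | 2.752 (+1.7%) | 86.6 to 89.5 | 87 to 90 |
| Already within, from Delta = 3 | 3.094 | 3.134 (+1.3%) | 113.2 to 116.1 | 114 to 117 |

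In the last row the overall SD is first rebuilt as sqrt(3.094^2 + 2.25), and 2 is then subtracted instead of 2.25. On the first row, power at 102 moves from 90.2% to 89.8%. A t-based calculation on that row gives 105 both before and after.

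**VL MFF with the 2:1 term (Delta = 3.63).**
- 5.941 as overall: SD 5.657 to 5.689 (+0.6%). At 80% power N is 85.8 to 86.8 unrounded, 87 in blocks both times. At 90% it is 114.8 to 116.1, 117 both times.
- 5.941 as within: SD 5.941 to 5.972 (+0.5%). At 80% N is 94.6 to 95.6, 96 both times. At 90% it is 126.7 to 128.0, 129 both times.
- With t quantiles the 80% figures are still unchanged (90 and 99). The 90% figures each move by one block (117 to 120, 129 to 132).

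**Direction against the truth.** The pooled variance contains the true effect d, not the assumed Delta. The printed formula errs low when Delta^2/4 exceeds 2 x d^2/9, that is when d is below Delta x sqrt(9/8) = 1.06 x Delta.

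**The case against.** The strongest reply is that the error is swamped by other uncertainty. Only 37 subjects had 18-month data at the interim, so the SD has a relative standard error of about 1/sqrt(2 x 36) = 12%, with a normal-theory 95% range of roughly 2.5 to 4.0 s. A correction of 0.65% to 1.7% is minor beside that. It is also minor beside two open questions in the same text: whether 3.094 s is overall or within-treatment, and whether Delta was 3 or 2. With Delta = 3 and a true effect of 2 s, the formula over-subtracts 2.25 - 0.89 = 1.36 s^2, and only 0.25 s^2 of that comes from the allocation term. All of this stands, and it sets the weight of the point. It does not make the formula right.

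A second reply is that the re-estimation was done in January 2020, so rewriting the formula would overwrite the record of the rule that was specified. That is fair, and a dated note would meet it.

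Three stronger readings are tempting, and the documents do not support them:
- A reader might infer that the VL MFF sample size was understated too. Its SD is, slightly. But the re-estimation set no VL MFF size, and the 80% requirement of 87 or 96 is unchanged and lies below both 99 and 110.
- A reader might infer that the SD is bound to be too low. That holds against the 2:1 formula at the same Delta. Against the true SD it fails once the true effect exceeds about 1.06 x Delta.
- A reader might blame this term for the reduction from 192 to 102. As written, with Delta = 3, the rule gives 87. The reduction came from a much smaller SD, partly offset by lowering the target from 3 s to 2 s.

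**Conclusion.** The formula is the 1:1 form and does not fit this 2:1 trial, for either endpoint. For the same assumed Delta it gives a within-treatment SD about 0.65% to 1.7% low for 4SC and 0.5% to 0.6% low for VL MFF. In unrounded terms the 4SC requirement rises by about 1.3 to 3 patients. On the only 2:1 route found to N=102, power is 89.8% instead of the claimed 90%. Allowing for 8% dropout, 110 randomised leaves 110 x 0.92 = 101.2 evaluable, so there is no spare margin, but the shortfall is under half a power point.

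This rests on a normal approximation, equal variances in the two arms, and, for the power figure, on 3.094 s being the overall SD with Delta = 2. Four places in the documents call it within-treatment, so the exact consequence stays open until the label is settled. The point is a correction to the method and its record. It does not threaten the trial's conclusions.

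**What to change.** - Replace (Delta/2)^2 by 2 x Delta^2 / 9 for both endpoints in the Protocol synopsis, Protocol 13.10.1 and SAP 2.6. Because the re-estimation was done in January 2020, the alternative is to leave the historical rule in place and record the correction in a dated note.
- State whether 3.094 s and 5.941% are overall or within-treatment SDs, and use one label throughout.
- State which Delta was subtracted for 4SC, 3 s or 2 s.
- Restate the 4SC power at N=102 on that basis: 89.8% if 3.094 s is overall and Delta was 2.

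The cost is some wording and one recalculation. The stated 4SC power becomes slightly less favourable. No extra patients are needed, and the primary analysis does not change.
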